| Duration of study for each subject | 
Up to 60 months
 
Subjects will participate in up to 3 possible study visits over a total of 5 years. Duration of time since vaccination as part of CTN 236 varies depending on when they were enrolled; therefore, to ensure all subjects are offered participation in the long term follow up, 6 possible visit times have been created.
 |
| Visit schedule | Main Study Procedures (no standard clinical or sub-study procedures) |

| | Informed Consent/ Assent | Health Questionnaire | Study Blood Work | Cytology and HPV DNA & vaginal swabs* | SAE and Con Med Assessment |
|------------------------|-----------------------------|----------------------|------------------|---------------------------------------|----------------------------|
| Month 36 (Visit 8) | X | X | X | X | X |
| Month 48 (Visit 9) | X | X | X | X | X |
| Month 60 (Visit 10) | X | X | X | X | X |
| Month 72 (Visit 11) | X | X | X | X | X |
| Month 84 (Visit 12) | X | X | X | X | X |
| Month 96 (Visit 13) | X | X | X | X | X |

* Those girls and women who are pre-menarchal or never sexually active will not have any pelvic examinations, clinical Pap smears, or study genital sampling until post-menarchal and sexually active.

Complete outline of all procedures found in table 7.3

| | |
|--|---|
| Data collection | Template recruitment documents, consent and source documents will be provided by the Study Coordinating Centre. Source data will be transferred to paper case report forms and sent to the CIHR Canadian HIV Trials Network (CTN) where it will be entered into an electronic database. |
| Monitoring | This study is being conducted according to the following: International Committee on Harmonization (ICH) Guidance Document E6: Good Clinical Practice (GCP): Consolidated Guidelines. Site monitoring will be performed to ensure compliance with the above. |
| Data Safety Monitoring Board (DSMB) | The established CTN data safety monitoring committee with additional expertise in pediatrics and gyne-oncology will provide oversight and monitoring of the conduct of the study to ensure the safety of the subjects. Additionally, the DSMB will ensure the validity and integrity of the study data. |

LIST OF ABBREVIATIONS

| | |
|--------------|---|
| AE | Adverse event |
| AIDS | Acquired immunodeficiency syndrome |
| ART | Antiretroviral therapy |
| ARV | Antiretroviral |
| BCCDC | British Columbia Centre for Disease Control |

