7.5.7.2 Vaginal Samples for Microbiota Analyses

Vaginal samples should be collected during the speculum exam. Samples will be obtained using a Dacron swab. Remove study swab from kit and unscrew cap from red top tube. Insert swab into the vaginal canal and gently brush the swab against the surface of the vaginal wall. Rotate the swab clockwise approximately 3 times during collection to ensure adequate cell sampling. Remove swab and place into empty tube. Break off the swab shaft at the score even with the top of the tube. Align the shaft with the hole inside the tube cap and push down tightly over the shaft, sealing the tube. Screw red cap on. Repeat process with second swab. Refrigerate at 4°C and transfer to -20°C as soon as possible. Complete the sample collection log to indicate date and time swabs are transferred to refrigerator and/or freezer.

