11.0 SUBJECT COMPLETION AND WITHDRAWAL

Investigators or their delegates will attempt to contact those study subjects who do not return for study visits. Study personnel will make at least three attempts to contact the subject using various communication means. Each attempt should be documented in the subject source documents.

A subject completing three annual visits up to and including Month 96/Visit 13 will be considered to have completed the study.

Withdrawals will not be replaced. All withdrawals will be documented including the date of the withdrawal and the reason.

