notably the BiodiversityR, 134 vegan, 135 and ALDeX2136 packages, we will apply statistical and graphical techniques to identify patterns of bacterial diversity that are associated with HPV infection and disease. Specifically, we will use compositional analysis as implemented in ALDeX2 to test for relationships between specific bacterial taxa and HPV infection and cervical dysplasia in addition to other clinical variables at each time point. Taxa thus identified will be examined for changes in relative abundance across time using mixed-effects models to control for multiple measures on each subject, and comparing to HPV infection status, HPV type and other clinical and HIV correlates. We will also use hierarchical clustering methods to determine if the bacterial communities form identifiable and robust clusters, with particular species occurring more often together. We can then test if these clusters are associated with HPV infection, burden of infection (single vs. multiple types) and evidence of cervical disease using standard statistical tests such as logistic regression and ANOVA. Finally, we will use mixed-effects models to test for changes in bacterial diversity and species richness that are associated with HPV infection, burden of infection (i.e. infection with multiple HPV types) and evidence of cervical disease while controlling for repeated measures on each subject.

HIV and Lower Urinary Tract Symptoms Analysis. Descriptive statistics will be used for baseline patient characteristics. Logistic regression analysis will be performed to determine the effect of: severity of HIV (CD4 count, viral load, AIDS criteria met), current HIV medications, time since HIV diagnosis, and vaginal microbiome on lower urinary tract symptoms, while also considering the effects of age, parity, ethnicity, sexual practices (from various questions in the HPV in HIV questionnaire), history of STI, history of UTI, smoking status, alcohol use, drug use.

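### The bacterial-cluster tests do not say how repeat visits by the same woman are handled; if visits are pooled, ordinary logistic regression and ANOVA can overstate significance

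*Combined protocol and SAP*

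**What the plan says.** The vaginal microbiota paragraph of section 16.3 describes four analyses.

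1. ALDeX2 relates single taxa to HPV infection and dysplasia, "in addition to other clinical variables at each time point".
2. The taxa so found are followed over time "using mixed-effects models to control for multiple measures on each subject".
3. Hierarchical clustering looks for community clusters, whose associations are then tested. The sentence opens with "We can then test if these clusters are associated with HPV infection, burden of infection (single vs. multiple types" and closes with "evidence of cervical disease using standard statistical tests such as logistic regression and ANOVA".
4. Diversity and species richness are modelled with mixed effects "while controlling for repeated measures on each subject".

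Repeat sampling is part of the design. The Summary says "Subjects will participate in up to 3 possible study visits over a total of 5 years", and section 11.0 says "A subject completing three annual visits up to and including Month 96/Visit 13 will be considered to have completed the study". The table in section 7.3 and the outlines in section 7.4.3 schedule vaginal samples at every visit for eligible women. Each visit yields two swabs (section 7.5.7.2: "Repeat process with second swab"); the plan does not say whether both are sequenced.

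**The concern.** Logistic regression and ANOVA in their ordinary form treat every observation as independent. Samples from one woman a year apart may not be. HPV persistence is itself a study endpoint (section 3.0), and the Background (item 5) reports persistent infection in 41.5% of women in an international HIV-positive study. If a woman's bacterial cluster also tends to stay the same, three visits carry less information about the association than three separate women would, and an ordinary test on pooled visits understates the standard error.

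At stake is exploratory objective 2, which relates microbiome profiles to HPV acquisition or persistence and to dysplasia. The Background (item 6) looks ahead to individual cancer-risk profiling from such data, so a false cluster association could be carried forward.

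**Working it through.** The plan gives no sample size, significance level or ICC for the microbiota analyses, so there is no planned figure to reproduce. The check asks what happens to a nominal 5% test if all visits are pooled.

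**Inputs from the documents**
- Visits per woman: up to 3 (Summary; section 11.0).
- Outcome prevalence for illustration: 29% with at least one oncogenic HPV type at screening in the parent study (Background, item 10).
- Cohort offered participation: 407 (section 5.0). The number who will give genital samples is not stated.

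**Assumptions, not in the documents**
- Two-sided test at 0.05.
- One binary cluster contrast with 40% prevalence.
- ICCs on the observed yes/no scale of 0 to 1.
- Simulated cohorts of 200 and 400 women.
- The same number of visits from every woman, and one sample per visit.

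**Formulas**

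Design effect: DE = 1 + (m − 1) × ICC(cluster) × ICC(outcome), where m is visits per woman.

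True type I error = 2 × [1 − Φ(1.96/√DE)].

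Worked case, m = 3 and both ICCs 0.5: DE = 1 + 2 × 0.5 × 0.5 = 1.50; 1.96/√1.50 = 1.600; error = 0.1095.

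| ICC cluster / outcome | DE, 3 visits | Error, 3 visits | Simulated ordinary logistic, 200 / 400 women | Error, 2 visits |
|---|---|---|---|---|
| 0 / 0.5 | 1.00 | 0.0500 | 0.0525 / 0.0535 | 0.0500 |
| 0.3 / 0.3 | 1.18 | 0.0712 | 0.0645 / 0.0670 | 0.0605 |
| 0.5 / 0.5 | 1.50 | 0.1095 | 0.1095 / 0.1155 | 0.0796 |
| 0.7 / 0.7 | 1.98 | 0.1637 | 0.1610 / 0.1720 | 0.1083 |
| 1 / 0.7 | 2.40 | 0.2058 | not run | 0.1328 |

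The simulations used 2,000 data sets per setting with no true association and three visits per woman. Realised ICCs were within 0.02 of the tabled values, except in the first row, where the outcome ICC was about 0.39. The Monte Carlo standard error at 0.05 is √(0.05 × 0.95/2000) = 0.005, so formula and simulation agree well.

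**Remedies in the same simulations**
- All three visits with a woman-level robust standard error: 0.044 to 0.055.
- Ordinary logistic regression on one visit per woman: 0.0435 to 0.0545.

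Both are close to nominal. Using all visits keeps more information: three visits are worth 3/DE independent observations per woman, that is 3/1.18 = 2.54, 3/1.50 = 2.00 and 3/1.98 = 1.52 for ICCs of 0.3, 0.5 and 0.7, against 1 for a single visit.

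**The case against.** The plan never says that visits are pooled for the cluster step. The first analysis in the same paragraph is run separately at each time point. If the cluster tests follow that pattern, each woman enters each test once and the ordinary methods are valid. The two mixed-model steps concern change, whereas the cluster sentence has no time element, so a division into cross-sectional tests and models of change is a coherent reading. The wording is also permissive, the tests are given only as examples, and even the unit being clustered is not stated. The ICCs are unknown, and with no persistence of cluster membership there is no inflation. The analysis is exploratory, with no significance level attached.

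Most of this stands. A reader might infer that the cluster p-values are bound to be too small, or that the authors overlooked repeated measures. The documents support neither: pooling is not stated, and the same paragraph deals with repeat visits elsewhere. Nor should the design be read as three swabs per woman; it is up to three visits with two swabs each.

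The objection does not remove the gap. The phrase about time points belongs to the ALDeX2 sentence and is not repeated for clusters. Read per visit, the plan would spread each outcome over up to six smaller tests, one for each scheduled month from 36 to 96, with no rule for combining them. The sentence needs an edit on either reading.

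**Conclusion.** The concern holds conditionally. As written, the cluster step names tests that make no allowance for within-woman correlation and does not limit them to one visit per woman. Too many false positives would follow only if visits are pooled and both cluster membership and the outcome persist. Some HPV persistence is supported by the documents; persistence of bacterial clusters is an assumption.

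With three visits and both ICCs between 0.3 and 0.7, the true error of a nominal 5% test is about 7% to 16%; with two visits it is about 6% to 11%. Women with fewer visits would pull the three-visit figures down. These figures are for a single binary contrast; a test across several clusters was not examined, nor was entry of both swabs from a visit. The point is confined to an exploratory objective and leaves the primary antibody analyses untouched.

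**What to change.** Replace the choice of tests in the cluster sentence of section 16.3 with text such as: *Associations of community cluster with HPV infection, burden of infection and cervical disease will be estimated from all visits, using logistic GEE with robust variance clustered on participant, or mixed-effects logistic or linear models with a participant random intercept. Where ordinary logistic regression or ANOVA is used, each test will include one visit per woman.*

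Choose between GEE and mixed models in advance, because their odds ratios answer different questions (population-average and within-participant). State the unit that is clustered, and whether one or both swabs per visit enter the analysis.

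The plan already uses GEE in section 16.2(c) and mixed models in section 16.3, so no new methods or data are needed. Compared with an ordinary pooled analysis, intervals widen by about √DE: √1.18 = 1.09, √1.50 = 1.22 and √1.98 = 1.41 in the three settings. That is the loss of precision the pooled analysis would have hidden.

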7.5.7.4 Lower Urinary Tract Symptoms Survey

The objective of this survey is to further investigate the prevalence and impact of lower urinary tract symptoms in cohort participants above the age of 18. This survey is a one-time cross sectional measure comprised of 14 questions, to be administered at one study visit per participant; questions may be answered at any of the 6 possible study visits and will take 10 – 15 minutes to complete.

The survey is comprised of 14 questions and includes two validated instruments.⁸⁵ The Urogenital Distress Inventory 6 (UDI-6) asks questions about certain bladder symptoms and how much participants are bothered by them. The Urinary Incontinence Questionnaire 7 (UIQ-7), ask questions about how much these symptoms affect participants' activities of daily living. This study questionnaire concludes with one supplementary question regarding prevalence of urinary tract infections in the past year. Inclusion of this survey will provide a greater understanding of gynaecological health in this cohort and speak to any relation between HPV infection and urogenital distress.

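### The urinary-symptom survey collects graded bother and impact scores, but the only model named is a logistic regression on an undefined outcome; the graded scores should be the outcomes for the association analyses.

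*Combined protocol and SAP*

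**What the plan says.** Section 7.5.7.4 (Lower Urinary Tract Symptoms Survey) gives the aim as "to further investigate the prevalence and impact of lower urinary tract symptoms in cohort participants above the age of 18". On content it says: "The survey is comprised of 14 questions and includes two validated instruments". The UDI-6 "asks questions about certain bladder symptoms and how much participants are bothered by them", and the UIQ-7 items "ask questions about how much these symptoms affect participants' activities of daily living". One further question asks about urinary tract infections in the past year. Each participant answers once.

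Section 16.3 (Exploratory Analyses, paragraph on HIV and lower urinary tract symptoms) plans descriptive statistics for baseline characteristics and then one model: "Logistic regression analysis will be performed to determine the effect of: severity of HIV (CD4 count, viral load, AIDS criteria met), current HIV medications". The exposure list ends with "time since HIV diagnosis, and vaginal microbiome on lower urinary tract symptoms", and those last words are the only description of the outcome. Adjustment variables follow, beginning with "age, parity, ethnicity, sexual practices (from various questions in the HPV in HIV questionnaire" and continuing with past infections, smoking, alcohol and drug use.

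Neither section says how the instruments are scored, which score is modelled, what makes a woman a case, or whether the logistic model is binary or ordinal.

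**The concern.** Thirteen of the 14 questions belong to instruments that ask about degree. Half of the stated aim, impact, is a matter of degree too. A logistic regression with no further qualification is normally a model for a yes/no outcome. Under that reading, a woman with slight bother and a woman with severe bother fall in the same class, or are separated only by where an unstated cut-off happens to lie.

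Two things are at stake. First, associations of HIV severity with symptoms become harder to detect, and because each woman is surveyed once, repeat measurements cannot recover what is lost. Second, a cut-off that is not fixed beforehand can be chosen after the data are seen.

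**Working it through.** **Inputs from the documents**
- Survey items (7.5.7.4): 6 (UDI-6) + 7 (UIQ-7) + 1 = 14, which agrees with the stated 14.
- Women available: 407 offered participation (5.0), with 94% still engaged in the parent study (4.0, Rationale): 0.94 × 407 ≈ 383. This is an upper bound for the survey, which covers only those above 18.
- Score distribution, prevalence, cut-off, expected number of cases, target power: none given. There is no figure in the plan to reproduce, so everything below rests on stated assumptions.

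**1. How the plan uses model names.** Section 16.2(d) uses logistic regression for HPV seroresponse, a yes/no outcome. Section 16.3 allows either linear or logistic models for the HSV-2 analyses, according to the outcome. The microbiota paragraph names ANOVA and mixed-effects models. The urinary paragraph has no such alternative, so binary is the natural reading.

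**2. Roughly normal score, cut so that a proportion p are cases.** Information kept, relative to the uncut score, is φ(z_p)² / [p(1−p)]. Its inverse is the factor by which the sample would have to grow.

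| p | Kept | Lost | Sample-size factor |
|---|---|---|---|
| 50% | 0.637 | 36% | 1.57 |
| 30% | 0.576 | 42% | 1.74 |
| 20% | 0.490 | 51% | 2.04 |
| 10% | 0.342 | 66% | 2.92 |

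**3. Near-continuous score under proportional odds.** The ordinal information is proportional to (1 − Σp_k³)/3, where p_k is the share at level k. The binary information is proportional to p(1−p). With many levels Σp_k³ is close to zero, so the share kept is 3p(1−p): 0.75, 0.63, 0.48 and 0.27 at p = 50%, 30%, 20% and 10%. The losses are 25%, 37%, 52% and 73%.

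**4. Many women scoring zero.** Assume a share f at zero and the rest spread evenly over 18 higher levels. Share kept = p(1−p) / [(1 − Σp_k³)/3].
- Cut at any versus none. For f = 70%: 0.70 × 0.30 = 0.210; (1 − 0.343 − 0.0001)/3 = 0.219; kept 0.959, lost 4%. For f = 50% the loss is 14%, and for f = 30% it is 35%.
- Cut halfway up the non-zero scores: losses of 30%, 36% and 42% for f = 30%, 50% and 70%.

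So the same data with 70% at zero lose 4% or 42%, depending only on the cut-off that the plan leaves open.

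**5. Illustration as power.** Assume a normal score, two equal groups, N = 383 in total, a difference of 0.3 SD and two-sided α = 0.05. With the graded score, power = Φ(0.3 × √(191.5/2) − 1.96) = Φ(0.976) = 84%. After a yes/no split (two-proportion test) it is 65%, 60%, 53% and 40% at p = 50%, 30%, 20% and 10%.

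**The case against.** The strongest reply is that the plan never says the scores will be dichotomised. Ordinal logistic regression is a logistic regression, so the proposed remedy even fits the present wording. That stands as far as it goes: the yes/no outcome is the ordinary reading and not a documented decision. What the text does show is an undefined outcome, and stating the ordinal model settles the matter under either reading.

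A yes/no outcome also suits the prevalence half of the aim. That is accepted, and the fix keeps one for that purpose.

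Three stronger readings are tempting, and the documents do not support them.
- A reader might infer that a third to two thirds of the information is certain to be lost. That range needs a normal score and a cut between 50% and 10%. If most women score zero and the cut is any versus none, the loss may be only about 4%.
- A reader might infer that impact has no analysis at all. Because the outcome is undefined, the UIQ-7 is neither included nor excluded. What can be said is that no analysis of impact as measured is specified.
- A reader might infer that more than 15 predictors are planned. Section 16.3 names 6 exposures and 9 adjustment variables, which is 15. Some will need several parameters once coded, but changing the outcome does not alter that list, so it forms no part of this point.

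Finally, the survey is a one-time addition, is analysed under Exploratory Analyses, and is absent from the objectives in section 3.0. That limits the importance of the point but does not remove it.

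**Conclusion.** The point holds as a choice of analysis that can be improved. Two graded instruments and an aim that includes impact are matched with one model which, as ordinarily read, does not use the grading, and the outcome is not defined. The size of the loss is assumption-based: 36% to 66% for a roughly normal score cut between 50% and 10%, and about 4% to 73% across all the shapes tried. That wider range covers the scenarios shown and is not a bound; a more extreme cut or a heavier pile-up at zero would go beyond it. No primary or secondary conclusion is affected.

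**What to change.** In section 16.3, state that the outcomes for the association analyses are the UDI-6 total score and the UIQ-7 total score, each analysed by proportional-odds (ordinal) regression on the exposures and adjustment variables already listed. This model uses the whole scale and copes with many zero scores. State how each total is formed. Keep a yes/no symptom variable, with its case definition written down before the data are examined, to report prevalence with a 95% interval.

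The cost is a sentence or two in 16.3 and no new data. The downside is that results come as ordinal odds ratios, which are less familiar to some readers, and that the proportional-odds assumption must be checked and the check reported.

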17.0 DATA MANAGEMENT

Data management will be performed by the CIHR Canadian HIV Trials Network (CTN).

Source document data will be transferred to a case report form by study personnel at the investigative sites. The participant identification number (PID) and a unique 3 letter code that was assigned in CTN 236 will be used to label the case report form and all study samples.

Data will be entered into a relational database with pre-programmed quality assurance checks. Queries will be resolved with the site study coordinator, with appropriate documentation. Data edits will be checked by the CTN data manager before being added to the master database. Backup copies of the database will be made daily and stored securely at a second location. No personal identifiers will be included in the database. Analysis will be conducted using statistical software (e.g. SAS or SPSS).

All personal information pertaining to participants will be securely stored at sites in a locked room, under the supervision of the site study coordinator(s) and accessible to study staff only. Where electronic databases are used as mechanisms for subject tracking etc. these databases will be password protected and available only to specified study staff and site investigators.

